7. I am presently wor	rrying over possible misfortunes	1	2	3	4
8. I feel satisfied		1	2	3	4
9. I feel frightened		1	2	3	4
10. I feel comfortable.		1	2	3	4
11. I feel self-confiden	t,	1	2	3	4
12. I feel nervous		1	2	3	4
13. I am jittery		1	2	3	4
14. I feel indecisive		1	2	3	4
15. I am relaxed		1	2	3	4
16. I feel content		1	2	3	4
17. I am worried		1	2	3	4
18. I feel confused		1	2	3	4
19. I feel steady		1	2	3	4
20. I feel pleasant		1	2	3	4
	,1977 by Charles D. Spielberger. All rights reserved. Published by Mind Garden, Inc., Redwood City, CA.	STAIP-AD 1	_		

Date: March 2, 2022

Principal Investigator: [name].

*#+7) Snaith-Hamilton pleasure scale (Snaith et al., 1995) is designed to measure hedonic tone. Subjects indicate the extent to which they agree or disagree with a series of statements relating to their expected enjoyment of a range of normally pleasurable events.

Directions: This questionnaire is designed to measure your ability to experience pleasure during your current abstinence period. It is important to read each statement very carefully. Check one of the boxes [] to indicate how much you agree or disagree with each statement.

For each item:	[] strong	ly disagree	[] disagree	e [] agree	[] strongly agree

- 1) I would enjoy my favorite television or radio program:
- 2) I would enjoy being with my family or close friends:
- 3) I would find pleasure in my hobbies and pastimes:
- 4) I would be able to enjoy my favorite meal:
- 5) I would enjoy a warm bath or refreshing shower:
- 6) I would find pleasure in the scent of flowers or the smell of a fresh sea breeze or freshly baked bread:
- 7) I would enjoy seeing other people's smiling faces:
- 8) I would enjoy looking "smart" when I have made and effort with my appearance:
- 9) I would enjoy reading a book, magazine, or newspaper:
- 10) I would enjoy a cup of tea or coffee or my favorite drink:
- 11) I would find pleasure in small things, e.g., bright sunny day, a telephone call from a friend:
- 12) I would be able to enjoy a beautiful landscape or view:
- 13) I would get pleasure from helping others:
- 14) I would feel pleasure when I receive praise from other people:

Principal Investigator: [name].

*8) Time-line followback. (TLFB). The TLFB will be used to assess smoking behavior since last an individual's last treatment visit (e.g., 7 days). Participants will read the instructions and will be guided by the therapist in filling out the calendar.

Date: March 2, 2022

Principal Investigator: [name].

Instructions for Filling Out the Timeline Cigarette Use Calendar

To help us evaluate your cigarette use, we need to get an idea of what your smoking was like in the past ____ days. To do this, we would like you to fill out the attached calendar.

- ✓ Filling out the calendar is not hard!
- ✓ Try to be as accurate as possible.
- ✓ We recognize you won't have perfect recall. That's OKAY.

✓ WHAT TO FILL IN

- The idea is to record how many cigarettes you smoked for each day on the calendar.
- On days when you did not smoke cigarettes, not even one, you should write a "0."

It's important that something is written for every day, even if it is a "0".

√ YOUR BEST ESTIMATE

- We realize it isn't easy to recall things with 100% accuracy.
- If you are not sure whether you smoked 15 or 16 cigarettes or whether you smoked on a Thursday or a Friday, give it your best guess! What is important is that 15 or 16 cigarettes is very different from 1 cigarette. The goal is to get a sense of how frequently you smoked, how much you smoked, and your patterns of smoking.

✓ HELPFUL HINTS

- If you have an appointment book you can use it to help you recall your use.
- Holidays such as Thanksgiving and Christmas are marked on the calendar to help you recall your smoking. Also, think about how much you smoked on personal holidays & events such as birthdays, vacations, or parties.
- If you have **regular patterns to your smoking**, you can use these to help you recall your use. For example, some people may only smoke during social situations.

✓ COMPLETING THE CALENDAR

Date: March 2, 2022

Principal Investigator: [name].

each day.					,
 A blank calenda 	ar is attached	. Write in the	number o	of cigarettes	you smoked on

•	The time	period we	are t	alking	about	on	the	calendai	r is
---	----------	-----------	-------	--------	-------	----	-----	----------	------

from	to

- In estimating the number of cigarettes you smoked, be as accurate as possible.
- DOUBLE CHECK THAT ALL DAYS ARE FILLED IN BEFORE RETURNING THE CALENDAR.
- Before you start look at the **SAMPLE CALENDAR** on the next page.

Instructions for Filling Out the Timeline Cigarette Calendar

✓ SAMPLE CALENDAR

2000	SUN	MON	TUES	WED	THURS	FRI	SAT
						1	2
						20	0
S	3	4 Labor Day	5	6	7	8	9
	20	20	23	28	21	20	23
E	10	11	12	13	14	15	16
	20	20	20	28	25	0	24
Р	17	18	19	20	21	22	23
	20	20	20	20	22	22	24
l _	24	25	26	27	28	29	30
Т	21	22	26	24	23	0	22

CDW Entry (for investigator entry):

TLFB - Tobacco Cigarettes

Date of Last Visit:
Enter the number of cigarettes smoked per day since the last session, starting with
resterday and working backwards

Day 1 (yesterday)

Day 2

Day 3

Etc...

*#+9) Perceived Stress Scale (PSS; Cohen, Kamarck, & Mermelstein, 1983). The PSS is a brief instrument used to assess degree of perceived stress during the past month using 10 Likert-type items. Each item is rated on a 5-point scale from never to very often. Completion time: ~5min.

The questions in this scale ask you about your feelings and thoughts **during the last month**. In each case, you will be asked to indicate by circling *how often* you felt or thought a certain way.

0 = Never 1 = Almost Never 2 = Sometimes 3 = Fairly Often 4 = Very Often 1. In the last month, how often have you been upset 2. In the last month, how often have you felt that you were unable 4 3. In the last month, how often have you felt nervous and "stressed"? 0 1 2 3 4 4. In the last month, how often have you felt confident about your ability to handle your personal problems? 0 1 2 3 4 5. In the last month, how often have you felt that things 6. In the last month, how often have you found that you could not cope 7. In the last month, how often have you been able 4 8. In the last month, how often have you felt that you were on top of things?.... 0 1 2 34 9. In the last month, how often have you been angered 10. In the last month, how often have you felt difficulties

tDCS Arm Questionnaires

Date: March 2, 2022

The Minnesota Nicotine Withdrawal scale (Hughes and Hatsukami, 1998) yields a measure of total withdrawal related discomfort based on ratings from 15 self-report items. Completion time: ~5 min.

Directions: Please rate the degree to which you have experienced the following, over the past 24 hrs.

0=none, 1=slight, 2=mild, 3=moderate, 4=severe

1) Angry, Irritable, frustrated	0 1 2 3 4
2) Anxious, Nervous	0 1 2 3 4
3) Depressed mood, Sad	0 1 2 3 4
4) Desire or craving to smoke	0 1 2 3 4
5) Difficulty concentrating	0 1 2 3 4
6) Increased appetite	01234
7) Insomnia, sleep problems, awakening at night	0 1 2 3 4
8) Restless	0 1 2 3 4
9) Impatient	0 1 2 3 4
10) Constipation	0 1 2 3 4
11) Dizziness	0 1 2 3 4
12) Coughing	01234
13) Dreaming or Nightmares	0 1 2 3 4
14) Nausea	0 1 2 3 4
15) Sore throat	0 1 2 3 4

Date: March 2, 2022

Principal Investigator: [name].

Visual analog scales (100mm) will also be used to assess the degree to which various nicotine withdrawal symptoms may be experienced: depressed, clumsy, tired, anxious, happy, drowsy, sad, dizzy, alert, energetic, light-headed, irritable, frustrated, nervous, sad, desire to smoke, difficulty concentrating, increased appetite, hunger, weight-gain, difficultly sleeping, awakening at night, insomnia, restless, impatient, panicked, missing cigarettes, urge to smoke, disoriented. Completion time ~10 min.

(This Visual Analog Scale is a different version from the one given as part of the Main Study Arm.)

Not at all	Extreme	9

The Profile of Mood States (POMS) measures present mood state (disturbance) by a list of adjectives on a 5-point scale and measures six dimensions of affect or mood, including tension-anxiety, depression-dejection, anger-hostility, vigor-activity, fatigue-inertia, and confusion-bewilderment. The measure has been shown to produce reliable and valid profiles of mood state (McNair et al., ; Cella et al., 1989). Completion time ~10min.

Directions: Indicate HOW YOU FEEL RIGHT NOW by selecting one of the numbers on the 5-poit scale.

FEELING Friendly		Not at all	A little 2	Moderate 3	Quite a bit 4	Extremely 5
	Shaky Listless Peeved Considera Sad Active On edge Grouchy Blue Energetic Panicky Hopeless Relaxed Unworthy Spiteful Sympathe Uneasy Restless	ded hings done te concentrate		Lonely Miserable Muddled Cheerful Bitter Exhausted Anxious Ready to fig Good-nature Gloomy Desperate Sluggish Rebellious Helpless Weary Bewildered Alert Deceived Furious Efficacious Trusting Full of pep Bad-temper Worthless Forgetful Carefree Terrified Guilty Vigorous Uncertain al Bushed	ed	
	51 . 5 555					

Principal Investigator: [name].

The State-Trait Anxiety Inventory Form Y (STAI) is an instrument for measuring anxiety in adults. The STAI differentiates between the temporary condition of "state anxiety" and the more general and long-standing quality of "trait anxiety." The essential qualities evaluated by the STAI-anxiety scale are feelings of apprehension, tension, nervousness, and worry. Completion time: ~10min. The copy below includes the Trait Inventory (in addition to the State Inventory given in the Main Study Arm)

	SELF-EVALUATION QUESTIONNAIRE	STAI Fo	orm Y	-1	
Please provide th	e following information:	_			
Name		S		_	
Age	Gender (Circle) M F		Г	_	
	DIRECTIONS:	40	4		
Read each statement and o indicate how you feel rianswers. Do not spend to seems to describe your page.		Nor Sontent	ENTELY.	ANICH S	6
					4
			2	3	4
			2	3	4
			2	3	4
5. I feel at ease		1	2	3	4
			2	3	4
7. I am presently w	orrying over possible misfortunes	1	2	3	4
			2	3	4
9. I feel frightened.		1	2	3	4
10. I feel comfortable	e	1	2	3	4
11. I feel self-confide	ent	1	2	3	4
12. I feel nervous		1	2	3	4
13. I am jittery		1	2	3	4
14. I feel indecisive.		1	2	3	4
15. I am relaxed		1	2	3	4
16. I feel content		1	2	3	4
17. I am worried		1	2	3	4
18. I feel confused		1	2	3	4
19. I feel steady		1	2	3	4
20. I feel pleasant		1	2	3	4

Principal Investigator: [name].

SELF-EVALUATION QUESTIONNAIRE STAI Form Y-2

Name	_Date		_	
DIRECTIONS	The co	Z.	40	
A number of statements which people have used to describe themselves are given below. Read each statement and then circle the appropriate number to the right of the statement to indicate how you generally feel. There are no right or wrong answers. Do not spend too much time on any one statement but give the answer which seems to describe how you generally feel.	ALMOST ARLES	TIMES C	MOST RY	475
21. I feel pleasant	1	2	3	4
22. I feel nervous and restless	1	2	3	4
23. I feel satisfied with myself	1	2	3	4
24. I wish I could be as happy as others seem to be	1	2	3	4
25. I feel like a failure	1	2	3	4
26. I feel rested	1	2	3	4
27. I am "calm, cool, and collected"	1	2	3	4
28. I feel that difficulties are piling up so that I cannot overcome them	1	2	3	4
29. I worry too much over something that really doesn't matter	1	2	3	4
30. I am happy	1	2	3	4
31. I have disturbing thoughts	1	2	3	4
32. I lack self-confidence	1	2	3	4
33. I feel secure	1	2	3	4
34. I make decisions easily	1	2	3	4
35. I feel inadequate	1	2	3	4
36. I am content	1	2	3	4
37. Some unimportant thought runs through my mind and bothers me	1	2	3	4
38. I take disappointments so keenly that I can't put them out of my mind	1	2	3	4
39. I am a steady person	1	2	3	4
40. I get in a state of tension or turmoil as I think over my recent concerns and inte	rests 1	2	3	4

© Copyright 1968,1977 by Charles D. Spielberger. All rights reserved. STAIP-AD Test Form Y Published by Mind Garden, Inc., Redwood City, CA.

Date: March 2, 2022

Principal Investigator: [name].

Menstrual History Questionnaire Adapted from the Fernald Community Cohort/Medical Monitoring Program 2007 Questionnaire (Female). University of Cincinnati College of Medicine, Department of Environmental Health. https://med.uc.edu/docs/defaulthttps://med.uc.edu/eh/research/projects/fcc/questionnaire, source/Environmental-Health/fcc/y2007-questionnaire female.pdf?sfvrsn=0 1. How old were you when you started having menstrual periods? 1a. If you cannot remember your exact age, were you: □ Younger than 10 □ 16 or older □ 10-12 yrs old □ 13-15 yrs old □ Don't Know 2. At present which statement best describes your menstrual cycle? ☐ I'm still having regular periods: The date of my last period was: / / ☐ My periods are irregular: The date of my last period was: / / ☐ I'm pregnant, or my last pregnancy ended within the past 2 months, or I'm breast feeding □ My periods have stopped on their own. (I've had menopause.) ☐ I've had menopause, but now have periods because I am taking hormones. □ I've had an operation (surgery) which stopped my periods. If your menstrual periods ceased because of surgery, what did you have removed? □ One ovary only □ Uterus only □ Both ovaries □ Uterus and one ovary □ Uterus and both ovaries □ Don't know □ I've taken medication which has stopped my periods. If your periods stopped because of medication, which medication were you taking? Medication name: □ I"ve had chemotherapy which has stopped my periods. □ I've had radiation therapy which has stopped my periods.

3. If your menstrual periods have stopped, how old were you when your menstrual periods stopped? (Please provide us with the age at which your menstrual periods stopped regardless of why they have stopped – naturally, due to surgery, medication, chemotherapy, or radiation therapy. If your periods have stopped, but you now have periods because of taking hormones, answer with the age at which your periods first stopped.)

□ Other:

Principal Investigator: [name]. Were you: ☐ Younger than 20 □ 45-49 yrs old □ 20-29 yrs old \Box 50-54 yrs old □ 30-39 yrs old \Box 55 – 59 yrs old □ 40-44 yrs old \square 60 or older OR □ My menstrual periods have not stopped. 4. If your menstrual periods have stopped, how old were you when you first experienced symptoms of menopause such as hot flashes or night sweats? Years old □ Did not experience symptoms □ Don't Know OR □ My menstrual periods have not stopped. All women should answer the next two questions, whether they currently have menstrual periods or not. 5. When you are (were) having regular menstrual cycles, how many days are (were) there between periods? Days between periods For how many days do (did) you have your period? Days 6. Between the ages of 18 and 40, excluding times when you may have been on the pill, pregnant, or nursing, which of the following statements BEST describes your menstrual periods? They are (were)... □ Nearly always regular, that is, you could usually predict when you would start bleeding to within two or three days □ Fairly Regular □ Irregular □ Don't Know

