During both the nicotine-deprived and non-deprived abstinence period participants will use a small video camera to video record themselves measuring their CO levels. They will also report mood and withdrawal symptoms at 6 time points throughout each abstinence period: 10pm on day 1 (2hrs post-cessation); 8am on day 2 (12 hrs post-cessation); 12noon on day 2 (16 hrs post-cessation); 4pm on day 2 (20hrs post-cessation); 8pm on day 2 (24 hours post-cessation); 10pm on day 2 (26 hrs post-cessation). All times are approximate. Their CO levels will be measured again at 8am on day 3 (36 hrs post-abstinence) when they arrive at NIDA-IRP for their scanning session. Research staff will generally phone participants on the afternoon they are to commence their abstinence period. Participants may also receive text message reminders from research staff at each of the six measurement time-points depending on participant needs. This procedure will allow the research team to monitor participant CO levels throughout the 36 hr abstinence periods, validating smoking abstinence. It will also provide a method of measuring changes in mood and withdrawal symptoms throughout the 36 hr abstinence periods across both deprived and non-deprived conditions. This information will provide a measurement of responsivity to nicotine replacement.

Date: March 2, 2022

(iii) Scanning Visits.

There will be two scanning visits, both preceded by a 36 hr abstinence period. During one abstinence period and scanning session participants will wear a dose-matched nicotine patch. A placebo patch will be applied throughout the nicotine-deprived abstinence period and scanning session. The order of deprived and non-deprived sessions will be counterbalanced across subjects. Scanning sessions will be separated by a minimum of 5 days. The two scanning visits will be essentially identical. Each visit will consist of two 1.5 to 2 hr scanning sessions, one taking place in the morning (AM) and one in the afternoon (PM). Participants will also complete several preand post-scan tasks and a series of questionnaires throughout the day. All imaging visits will take approximately 9hrs (8am to 5pm) to complete. The order of procedures completed during each scan visit is outlined schematically in Figure 2, and described in detail below.

[figure not shown]

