11.2. Data-Analysis

Unless otherwise specified, all BOLD, genetic, behavioral, self-report and physiological data will be analyzed with AFNI or R (http://www.R-project.org; R Development Core Team, 2008). The types of statistical analysis to be utilized in the current protocol are summarized below.

Nicotine deprived vs non-deprived. Between condition (nicotine-deprived vs non-deprived) comparisons will be conducted on self-report, behavioral, BOLD ROI, resting CBF and ERP responses with a series of one-way repeated measures ANCOVAs, with nicotine-deprivation (nicotine-deprived vs non-deprived) as the within-subjects factor and nicotine dose as the covariate. By controlling for nicotine dose we can partially dissociate the

Principal Investigator: [name].

effects from acute nicotine-withdrawal effects. Treatment seeking status (Treatment seeking vs non-treatment seeking) will be included as a between-subjects factor in these models to assess the main effects and of motivation to quit as well as any interaction between motivation to quit and acute nicotine withdrawal.

Date: March 2, 2022

Mediation. Where mediation has been hypothesized (e.g., central CRF as a mediator of VS reactivity following acute nicotine withdrawal), regression coefficients for the paths of each mediation model will be derived with multiple regression and the mediation effect will be tested with ProdClin (Mackinnon, Fritz, Williams & Lockwood, 2007). ProdClin is a program developed by MacKinnon, Fritz, Williams, and Lockwood (2007) that uses the distribution of the product of paths a and b to compute asymmetric confidence intervals for the mediated effect. ProdClin is an alternative to the Sobel (1982) method that provides a more powerful and accurate test of the mediation effect because it is based on an asymmetric distribution which more closely resembles the true distribution of the product terms. Mediation models will be conducted separately for treatment-seeking and non-treatment seeking smokers.

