Appendix 4: State Measures (*administered during treatment sessions; #administered during scan sessions; + administered during follow-up scan sessions)

Date: March 2, 2022

*#+1) The Tobacco Craving Questionnaire (Singleton, Anderson, & Heishman, 2003) is a brief instrument used to assess current feelings related to smoking and craving using 12 Likert-type items. Each item is rated on a 7-point scale from strongly disagree to strongly agree. Completion time: ~10min.

Directions: Indicate how strongly you agree or disagree with each of the following statements by placing a check mark in one of the spaces between STRONGLY DISAGREE and STRONGLY AGREE. The closer you place your check mark to one end or the other indicates the strength of your agreement or disagreement. If you don't agree or disagree with a statement, place your check mark in the middle space. Please complete every item. We are interested in how you are thinking or feeling **right now** as you are filling out the questionnaire.

1. I would enjoy a cigarette ri	gnt now	· .					
STRONGLY DISAGREE _	:	_:_	:	:	:	:	_ STRONGLY AGREE
2. If I smoked right now, I wo	ould not	be able	e to sto	p.			
STRONGLY DISAGREE _	:	_:_	:	_:_	:	:	_ STRONGLY AGREE
3. If I had a lit cigarette in my	hand I	nroha	hly wo	uld sma	oke it		
STRONGLY DISAGREE						:	_ STRONGLY AGREE
4. A cigarette would taste goo	nd right 1	now					
STRONGLY DISAGREE			:_	:	:	:	_ STRONGLY AGREE
5. I would be less irritable nov	w if I co	aild em	noke				
STRONGLY DISAGREE				:	:	:	_ STRONGLY AGREE
6. It would be hard to pass up	the cha	nce to	cmoke				
STRONGLY DISAGREE					:	:	_ STRONGLY AGREE
7. Leaved not stop mysself from	m amalzi	ing if I	had so	ma aia	orottos	hara	
7. I could not stop myself from STRONGLY DISAGREE							STRONGLY AGREE
8. Smoking a cigarette would	ha place	ant					
STRONGLY DISAGREE			:	:	:	:	STRONGLY AGREE
9. If I were smoking now I co STRONGLY DISAGREE					:	:	STRONGLY AGREE
10. I would not be able to con STRONGLY DISAGREE						_	
11. I could not easily limit ho STRONGLY DISAGREE						:	STRONGLY AGREE
CNS IRB Protoc					·	·	SINGINGET HOREE

smoke Princi	cers.	[name]		Date: March 2, 2022
	control things better Y DISAGREE		: STRONGI	LY AGREE

*#+2) Tobacco Craving Scale consists of 5 self-report items pertaining to desire for a cigarette that are rated on a 10-point scales. Completion time: > 5 min.

Directions: Please circle the number on the scale that best describes your current feelings.

Date: March 2, 2022

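### The Perceived Stress Scale asks about the past month, so a deprived versus non-deprived contrast on it is largely insensitive to a 36-hour patch period

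*Combined protocol and SAP*

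**What the plan says.** **The scale.** Appendix 4 collects the state measures and uses symbols to show when each is given. The hash mark means "administered during scan sessions". The entry "9) Perceived Stress Scale" carries the hash, together with the marks for treatment sessions and follow-up scans, so the PSS is completed at both scan visits. The appendix describes it as "used to assess degree of perceived stress during the past month using 10 Likert-type items", and every printed item refers to the last month. Nothing in the protocol changes that window at scan visits.

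**The design.** Section 4.4 (iii) states: "There will be two scanning visits, both preceded by a 36 hr abstinence period". It adds "The order of deprived and non-deprived sessions will be counterbalanced across subjects" and "Scanning sessions will be separated by a minimum of 5 days". Section 4.1 gives about 3 to 5 weeks for orientation plus both scans. The debriefing text in Section 4.4 allows for a second scan a week or two after the first.

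**The analysis.** For the two patch conditions, Section 11.2 says that "comparisons will be conducted on self-report, behavioral, BOLD ROI, resting CBF and ERP responses", using repeated-measures ANCOVA. No questionnaire is excluded. Section 4.4 presents the scan-day questionnaires as measures of current state.

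**The neighbouring scales.** The Snaith-Hamilton form is "designed to measure your ability to experience pleasure", and its directions tie this to the abstinence period in progress. The Wisconsin withdrawal scale covers 24 hours. The PANAS, the state form of the STAI and the visual analog ratings ask about the present moment.

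**The concern.** The exposure lasts 1.5 days and the questionnaire looks back about 30. Two things then weaken the contrast. First, the patch period is a small part of each recall window. Second, with a short gap the second window also contains the first visit's patch period. A participant who was deprived first therefore reports on the same deprived days at both visits.

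What is at stake is how one planned self-report result is interpreted. A PSS difference near zero would be expected even if withdrawal raised stress sharply for a day and a half. Nothing in Section 11.2 warns the analyst of that, so the result could be misread as showing that withdrawal does not affect stress.

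**Working it through.** **1. The plan's own figure.** Section 11.4 gives about 35 participants for the deprived versus non-deprived comparison, with d = 0.5, correlation 0.5, alpha 0.05 and power 0.80. The standardised paired difference is dz = d/√(2(1 − r)) = 0.5/√(2 × 0.5) = 0.5. A two-sided paired t-test then needs n = 34, and power at n = 35 is 0.82. The stated figure is reproduced. It is used below only as a yardstick.

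**2. Inputs.** Recall window W = 30 days (the past month, Appendix 4). Exposure 36 h = 1.5 days, minimum gap g = 5 days, order counterbalanced (all Section 4.4).

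**3. Overlap of the two windows** = (W − g)/W.

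| Gap (days) | Shared days | Overlap |
|---|---|---|
| 5 | 25 of 30 | 83% |
| 7 | 23 of 30 | 77% |
| 14 | 16 of 30 | 53% |
| 15 | 15 of 30 | 50% |
| 21 | 9 of 30 | 30% |
| 28 | 2 of 30 | 7% |

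Taking the month as 28 or 31 days moves the 5-day figure only to 82% or 84%.

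**4. Effect retained, equal weight on each day.** Assume that the score averages the 30 days, with deprived days shifted by δ and all other days at 0.

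- Deprived first: both windows hold the same 1.5 deprived days, so the contrast is 1.5/30 − 1.5/30 = 0. This holds for gaps up to 30 − 1.5 = 28.5 days.
- Deprived second: only the second window holds deprived days, so the contrast is 1.5/30 = 0.05δ.
- Mean over the two orders: (0 + 0.05)/2 = 0.025δ.

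With no overlap at all (gap above 30 days) both orders retain 5%, because 36 hours is still only 1.5/30 of the window.

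**5. Effect retained, recency weighting, 5-day gap.** Let the weight on a day halve every h days, truncated at 30 days. The weight on the interval from a to b days before completion is (2^(−a/h) − 2^(−b/h))/(1 − 2^(−30/h)). Deprived second retains w(0, 1.5). Deprived first retains w(0, 1.5) − w(5, 6.5).

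| Half-life (days) | Deprived first | Deprived second | Mean | Power, n = 35, d = 0.5 |
|---|---|---|---|---|
| Equal weights | 0% | 5% | 2.5% | 0.05 |
| 15 | 2% | 9% | 5% | 0.05 |
| 7 | 6% | 15% | 10% | 0.06 |
| 5 | 10% | 19% | 14% | 0.07 |
| 3 | 20% | 29% | 25% | 0.11 |
| 1 | 63% | 65% | 64% | 0.45 |

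Under equal weights, d = 0.5 becomes 0.5 × 0.025 = 0.0125. The power column holds the SD of the difference fixed. Overlapping windows would raise the between-visit correlation and shrink that SD, so these powers are illustrative.

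**The case against.** The strongest reply is that the PSS may never have been meant as a deprivation endpoint. It appears in no aim, hypothesis, outcome or power calculation, and its link to the contrast is the general word for self-report data in Section 11.2. It is also given at treatment visits and at the 1-, 6- and 12-month follow-up scans, where a past-month window is natural. This stands as a limit on the harm. It does not remove the mismatch: the protocol labels the scale a state measure, repeats it at both scans, and exempts nothing from the contrast.

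A reader might infer that a null PSS result would count against Aim 2. The documents do not support that. Aim 2 lists self-reported negative affect, craving, and imaging during the amygdala and shock tasks; perceived stress is not among its measures. The same scan visits already collect momentary ratings of feeling stressed and anxious, the state anxiety form and the PANAS.

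A reader might also infer that the contrast vanishes by construction. That depends on how respondents weight days. The PSS asks for frequency ratings, no document supports an equal-day average, and 2.5% is the lowest mean in the range examined. High overlap likewise depends on short gaps: the windows share half their days or less at gaps of 15 days or more. The protocol gives a minimum gap but no typical one.

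**Conclusion.** The point holds as a minor one. As written, the plan yields a deprived versus non-deprived PSS contrast that is largely insensitive to the manipulation. It retains 2.5% of the effect on average under equal weighting of days, and about 5% to 25% under recency half-lives of 15 to 3 days at a 5-day gap. Only a very short memory (a 1-day half-life, 64%) keeps most of the signal, and that would mean largely setting aside the printed instruction. These figures rest on the assumed weighting of days and a 30-day month. Longer gaps reduce the overlap but, under equal weighting, cannot lift retention above 5%.

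The consequence is one uninformative self-report comparison. The planned sample size and the contrasts on the named outcomes are unaffected.

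**What to change.** Keep the past-month wording. Give the PSS once before the scans, for example with the baseline questionnaires at orientation. Use that score as a background covariate and as the baseline for follow-up. State in Section 11.2 that the PSS is excluded from the deprived versus non-deprived comparison, and remove the scan-session mark from its entry in Appendix 4. The treatment and follow-up administrations can stay as they are.

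Rest the state-stress contrast on the momentary stressed and anxious ratings, the STAI state form and the PANAS, all already collected at scan visits. The cost is that one scale drops out of the contrast; in return there is one less form on scan days.

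Rewording the stem to cover the current abstinence period, as the Snaith-Hamilton form does, is second best. It would make the scale responsive to the patch period, but scan-day scores would no longer be comparable with published past-month norms or with the trial's own PSS scores at treatment and follow-up visits.
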